7.2.12 Concomitant Medications

Concomitant therapies are to be collected from signing of the consent form through the SFU period. Following the SFU visit, only medications taken for the treatment of ALL will be collected.

For concomitant therapies, the therapy name, indication, dose, unit, frequency, start date and stop date will be collected.

Concomitant medication collection requirements and instructions are included in the eCRF completion guidelines.

7.2.13 Definitions of Treatment Response

The treatment is defined to be efficacious, when the subject is stated to be in CR or in CRh* or CRi.

Hematological remissions are defined by the following criteria:

Complete Remission (CR):

- Less than or equal to 5% blasts in the BM
- No evidence of disease
- Full recovery of peripheral blood counts:
 - Platelets > 100,000/ μ l
 - ANC > 1,000/ μ l

Approved

Complete Remission with only Partial Hematological Recovery (CRh*):

- Less than or equal to 5% blasts in the BM
- No evidence of disease
- Partial recovery of peripheral blood counts:
 - Platelets > 50,000/ μ l and
 - ANC > 500/ μ l

Complete Remission with only incomplete blood count recovery (CRi):

- Less than or equal to 5% blasts in the BM
- No evidence of disease
- Partial recovery of peripheral blood counts:
 - Platelets >100,000/ μ l; or
 - ANC > 1000/ μ l

Subjects who will have achieved CR or CRh* or CRi within 2 cycles of treatment will receive up to 3 additional cycles of treatment for consolidation.

Blast free hypoplastic or aplastic BM:

- Less than or equal to 5% blasts in the BM
- No evidence of disease
- Insufficient recovery of peripheral counts: platelets \leq 50,000/ μ l and/or ANC \leq 500/ μ l

The onset of remission is defined by the date of the first aspiration/biopsy on which the remission was documented.

When criteria are met for both CRh* and CRi, CRh* should be reported. When criteria are met for both CRi and blast-free marrow, CRi should be reported.

Progressive Disease:

- An increase of at least 25%, or an absolute increase of at least 5,000 cells/ μ L (whichever is greater), in the number of circulating leukemia cells, development of extramedullary disease, or other laboratory or clinical evidence of progressive disease

Non-response:

- None of the above

Hematological Relapse:

- Proportion of blasts in BM > 5% or
- Blasts in peripheral blood after documented CR/CRh*

An extramedullary relapse will be assessed as hematological relapse.

The relapse will be analyzed by immuno-phenotyping whether it still fulfills the criteria for B-precursor ALL. The onset of relapse is defined by the date of the first sample on which relapse was documented.

All hematological assessments of BM will be reviewed in a central reference laboratory.

In the event of disease progression or hematological relapse within the treatment period, treatment will be terminated.

Extramedullary disease:

If clinical signs of extramedullary lesions are present, assessments will be performed according to Cheson criteria (Table 10). If computed tomography (CT) scans are conducted, this should be done according to standard clinical practice. If a CT scan has been performed within one month before start of blinatumomab treatment and if no clinical signs of a change of disease state have been observed, this assessment can be regarded as screening assessment.

**Table 10. Cheson Criteria for Evaluation of Extramedullary Disease
 (From Cheson et al. 2007)**

Response	Definition	Nodal Masses	Spleen, Liver	Bone Marrow
CR	Disappearance of all evidence of disease	(a) FDG-avid or PET positive prior to therapy; mass of any size permitted if PET negative (b) Variably FDG-avid or PET negative; regression to normal size on CT	Not palpable, nodules disappeared	Infiltrate cleared on repeat biopsy; if indeterminate by morphology, immunohistochemistry should be negative
PR	Regression of measurable disease and no new sites	≥ 50% decrease in SPD of up to 6 largest dominant masses; no increase in size of other nodes (a) FDG-avid or PET positive prior to therapy; one or more PET positive at previously involved site (b) Variably FDG-avid or PET negative; regression on CT	≥ 50% decrease in SPD of nodules (for single nodule in greatest transverse diameter); no increase in size of liver or spleen	Irrelevant if positive prior to therapy; cell type should be specified
SD	Failure to attain CR/PR or PD	
 FDG-avid or PET positive prior to therapy; PET positive at prior sites of disease and no new sites on CT or PET Variably FDG-avid or PET negative; no change in size of previous lesions on CT 		
Relapsed disease or PD	Any new lesion or increase by ≥ 50% of previously involved sites from nadir	Appearance of a new lesion(s) > 1.5 cm in any axis, ≥ 50% increase in SPD of more than one node, or ≥ 50% increase in longest diameter of a previously identified node > 1 cm in short axis Lesions PET positive if FDG-avid lymphoma or PET positive prior to therapy	> 50% increase from nadir in the SPD of any previous lesions	New or recurrent involvement

Abbreviations: CR, complete remission; FDG, [¹⁸F]fluorodeoxyglucose; PET, positron emission tomography; CT, computed tomography; PR, partial remission; SPD, sum of the product of the diameters; SD, stable disease; PD, progressive disease.

MRD response:

MRD < 10⁻⁴ leukemic cells detectable measured by flow cytometry.

Approved

MRD complete response:

No detectable leukemic cells by flow cytometry

MRD relapse:

Re-appearance of leukemic cells detectable by flow cytometry.

MRD progression:

Increase in the MRD level by one log as compared to the baseline level which is equal to a 10-fold increase in the number of MRD cells.

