Subjects eligible for alloHSCT always represent a selected group, who have to survive at least as long as the donor search is conducted. Salvage chemotherapy should be administered before alloHSCT, in order to reduce tumor load (Gökbuget and Hoelzer, 2011). In the MRC UK study, 120 subjects (20%) were eligible to undergo an alloHSCT after relapse, either autologous (n = 13), matched unrelated (n = 65), or matched related (n = 42). Survival rates after 2 years were 15% for auto graft, 16% for unrelated and 23% for sibling HSCT (Fielding et al, 2007).

The French group identified alloHSCT in second CR as favorable prognostic factor for OS. Five-year survival after alloHSCT was 25% ([Tavernier et al, 2007](#)).

In the [name] retrospective study, the subjects who underwent alloHSCT, the estimated 3-years OS in CAG, HD-CAG, hyper-CVAD groups were 20.9% ± 7.5%, 18.4% ± 5.5%, and 29.0% ± 3.8%, respectively ([Liu et al, 2015](#)).

Treatment and Prevention of Extramedullary Relapse

A small fraction of relapses in adult subjects with ALL have an extramedullary location, for example in the CNS or testes. In contrast to childhood ALL, the outcome for extramedullary relapse in adult subjects with ALL is not different from medullary relapse ([Tavernier et al, 2007](#); [Fielding et al, 2007](#)). If the relapse is treated only locally for example by intrathecal therapy, the extramedullary relapse is usually followed by medullary relapse. Therefore extramedullary relapse of ALL should always be considered as systemic disease and local therapy such as intrathecal treatment of CNS relapse should be combined with systemic chemotherapy. In subjects with medullary relapse CNS prophylaxis should be administered ([Gökbuget and Hoelzer, 2011](#)).

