6.6 Criteria for Blinatumomab Discontinuation

Treatment with blinatumomab should be discontinued in the event of any of the following:

- Hematological or extramedullary relapse subsequent to achieving $\leq 5\%$ BM blasts on protocol treatment
 - Exception: subjects who develop isolated CNS leukemia, relapse during treatment and who have not met the criteria for an event as defined above, may continue on study and receive additional CNS directed therapy in addition to their systemic protocol-specified therapy. Subjects should receive intrathecal chemotherapy until negative for CNS leukemia before starting blinatumomab.
- Failure to achieve BM response defined as $\leq 5\%$ blasts within 2 treatment cycles
- Occurrence of an adverse event which makes discontinuation from treatment necessary due to protocol specified safety criteria or desirable in the investigator's and/or the subject's opinion
- An infusion interruption of more than 2 weeks due to an adverse event related to blinatumomab (exception: in case of logistical difficulties, restart of treatment can be postponed for up to 7 additional days without resulting in permanent treatment discontinuation)
- Investigator's decision that a change of therapy (including immediate HSCT) is in the subject's best interest
- Administration of relevant non-permitted concomitant medications (as outlined in [Section 6.9](#))
- Investigator's decision that a subject does not benefit from treatment anymore, eg, non-response or development of progressive disease
- Intercurrent medical condition, which in the opinion of the investigator or the subject precludes further treatment of the subject
- Withdrawal of subject's consent to further study treatment

All reasons for treatment discontinuation will be documented in the eCRFs. If a subject fails to keep the appointments for study visits, the investigator will document the reason and circumstances as completely and accurately as possible.

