8.3 Reasons for Removal From Treatment or Study

8.3.1 Reasons for Removal From Treatment

Reasons for removal from protocol-required investigational product(s) or procedural assessments include any of the following:

- Protocol-specified criteria:
 - Hematological or extramedullary relapse subsequent to CR/CRh*/CRi on protocol treatment
 - Failure to achieve a BM response defined as $\leq 5\%$ blasts within 2 complete treatment cycles
 - Investigator decision that a change of therapy (eg, immediate HSCT) is in the subject's best interest
- subject request
- safety concern (eg, due to toxicity of protocol-specified therapy or other adverse event)
- decision by sponsor (other than subject request or safety concern)

- death
- lost to follow-up

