10.4.3 Secondary Efficacy Endpoint

The secondary efficacy endpoints include RFS, CR rate, CR/CRh*/CRi rate, alloHSCT rate, OS, MRD response rate, and time to a 10 point decrease from baseline in global health status/Quality of Life (QoL) using the EORTC QLQ-C30.

- RFS: RFS time will be calculated from the first onset of CR/CRh* within the 2 cycles until the documented hematological relapse, extra-medullary disease, or death due to any cause, whichever occurs first. The analysis is restricted to subjects who achieve CR/CRh* within 2 cycles of treatment. The subjects still alive and relapse-free will be censored at the date of last disease assessment. If the last disease assessment date is after the date that triggers the analysis, the subject will be censored at the analysis trigger date. Sensitivity analyses of RFS will be calculated similarly for those who achieve CR/CRh* and those who achieve CR/CRh*/CRi.
- CR rate within 2 cycles of treatment with blinatumomab: CR rate is defined as the proportion of subjects who achieve CR within 2 cycles of treatment with blinatumomab. Subjects without response assessment will be accounted for in the denominator when calculating the response rate.
- CR/CRh*/CRi rate within 2 cycles of treatment with blinatumomab: CR/CRh*/CRi rate is defined as the proportion of subjects who achieve CR/CRh*/CRi within 2 cycles of treatment with blinatumomab. Subjects without response assessment will be accounted for in the denominator when calculating the response rate.
- AlloHSCT rate: AlloHSCT rate is defined as the proportion of subjects undergoing alloHSCT among who achieve CR/CRh* after treatment with blinatumomab.
- Overall survival (OS): OS time will be calculated from the time of first infusion of blinatumomab until death due to any cause. Subjects still alive will be censored at the date last known to be alive. If the date last known to be alive is after the date that triggers the analysis, the subject will be censored at the analysis trigger date.
- MRD response rate within 2 cycles of treatment of blinatumomab: MRD response rate is defined as the proportion of subjects who achieve MRD response within 2 cycles of treatment with blinatumomab. Subjects without response assessment will be accounted for in the denominator when calculating the response rate.

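### Protocol 7.2.13 stops blinatumomab for the isolated CNS leukemia that 6.6 allows to continue, and the SAP relapse entry has no criterion for CNS leukemia found only in CSF

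*Protocol*

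**What the plan says.** **Treatment rules in the protocol**

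- Section 7.2.13, on relapse: "An extramedullary relapse will be assessed as hematological relapse".
- Section 7.2.13, on progressive disease, includes: "development of extramedullary disease, or other laboratory or clinical evidence of progressive disease".
- Section 7.2.13, on the consequence: "In the event of disease progression or hematological relapse within the treatment period, treatment will be terminated".
- Section 6.6 lists as its first reason for discontinuation: "Hematological or extramedullary relapse subsequent to achieving" a marrow blast count of 5% or less. Directly beneath is a labelled exception for subjects with isolated CNS leukemia "who have not met the criteria for an event as defined above, may continue on study and receive additional CNS directed therapy" alongside their systemic protocol treatment. They are to have intrathecal chemotherapy until the CNS is clear before blinatumomab is started.
- Section 8.3.1 gives as a reason for removal from treatment: "Hematological or extramedullary relapse subsequent to CR/CRh*/CRi on protocol treatment". The exception is not repeated there.
- Section 2.3 places the CNS among extramedullary sites: "A small fraction of relapses in adult subjects with ALL have an extramedullary location, for example in the CNS or testes".

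**RFS event**

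Protocol 10.4.3 and the RFS entry in SAP Section 6 use the same event list, with time running "until the documented hematological relapse, extra-medullary disease, or death due to any cause, whichever occurs first". The separate relapse-event entry in SAP Section 6 is narrower. It has a hematological branch (marrow or peripheral blood blasts) and an extramedullary branch, which requires a lesion that is new or has grown by 50% from nadir under the Cheson criteria.

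**The concern.** A subject on treatment with a clear marrow and a positive CSF sample falls under a mandatory stop in one section and a permission to continue in another. With about 25 centers planned (Protocol 3.2), one site could stop blinatumomab believing that it must, while another continues it, and each could cite the protocol.

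The analysis has a related problem. An analyst who programs from the SAP relapse-event entry could miss a relapse seen only in CSF, although the SAP's RFS entry counts extramedullary disease. The subject would then be carried as relapse-free until a later event or censoring.

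**Working it through.** The treatment conflict is a matter of text, so the sections are set side by side. The arithmetic at the end only scales the RFS point.

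**Step 1: does 7.2.13 reach isolated CNS leukemia?** Yes, by two routes.

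| Route in 7.2.13 | Classified as | Consequence |
|---|---|---|
| CNS relapse after remission (the CNS is extramedullary by 2.3) | Hematological relapse | Treatment ends |
| New CNS disease on treatment | Progressive disease | Treatment ends |

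Neither route carries an exception or a reference to 6.6.

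**Step 2: does 6.6 resolve it?** Not as worded. The exception requires that the subject has not met an event criterion stated above it. The only criterion above it is the relapse bullet, which already includes extramedullary relapse. Read literally, the isolated CNS relapse itself disqualifies the subject, and the exception could cover no one. The exception also sits only under the relapse bullet. Section 6.6 mentions progressive disease only as an example of an investigator's decision that the subject no longer benefits, so the second route is not addressed.

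**Step 3: is 8.3.1 a second conflict?** No. It is a list of possible reasons for removal. Leaving out the exception is an omission.

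**Step 4: does the SAP contradict the protocol on RFS?** No. The two RFS definitions match. The gap is within the SAP, between its RFS entry (extramedullary disease in general) and its relapse-event entry (lesions only). Protocol Table 10, the Cheson table, covers nodal masses, spleen and liver, and bone marrow, with no CSF item. CSF-only disease therefore fits neither branch of the relapse-event entry clearly.

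**Step 5: is the case foreseeable?** Yes. Exclusion 204 confirms CNS ALL by CSF analysis. Table 9 schedules lumbar puncture at the end of each treatment cycle, and Section 7.2.9 gives leukemic involvement as the reason for examining the fluid.

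**Step 6: how far could RFS move?** The documents give no CNS relapse rate, so this is an illustration. Inputs:

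- Median RFS 5.9 months, from MT103-211 (Protocol 2.5.2).
- Assumed: exponential RFS and 40 RFS events.
- Assumed: *n* missed CNS relapses, each followed by a counted event *d* months later, so the event count stays at 40.

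Exposure = 40 × 5.9 / ln 2 = 340.5 person-months.

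Median after delay = ln 2 × (340.5 + *n* × *d*) / 40.

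| *n* | *d* (months) | Median (months) | Change |
|---|---|---|---|
| 1 | 1 | 5.92 | +0.3% |
| 2 | 1 | 5.93 | +0.6% |
| 2 | 3 | 6.00 | +1.8% |
| 5 | 6 | 6.42 | +8.8% |

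The last row is an extreme case. The illustration does not cover a missed relapse that is censored with no later event.

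**The case against.** The strongest defence is that a specific rule overrides a general one. Section 6.6 is the section on stopping blinatumomab and carries an exception labelled as such; 7.2.13 is a definitions section with one general sentence on termination. The Amendment 3 rationale shows that the CNS provision was deliberate. On this view the condition in 6.6 naturally means no relapse other than the CNS disease, and the defect is a missing cross-reference. This is probably what the authors intended. It remains an inference, because no text gives 6.6 precedence, 7.2.13 is worded as mandatory, and the literal condition in 6.6 defeats its own exception.

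A second argument is that 6.6 only permits continuation and separately lets the investigator change therapy, so sites would differ even after a correction. That stands in part. Discretion would remain, and the correction removes only the reading that stopping is compulsory.

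A third argument is that the SAP point is nearly covered. The RFS entry already counts extramedullary disease, and 7.2.13 already dates relapse by the first sample that documents it. This is right as far as it goes, and it confines the SAP point to the lesion-only relapse-event entry. That entry still disagrees with the RFS entry beside it.

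Finally, the numerical effect is small and rests on assumptions. That is accepted. Active CNS ALL is excluded at entry, intrathecal prophylaxis is mandatory unless lumbar puncture is unsafe, and RFS is a descriptive secondary endpoint.

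**Conclusion.** The concern holds. The protocol contains two incompatible instructions for isolated CNS leukemia on treatment, and nothing in either document says which governs. Patient management is the main reason to correct it.

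The SAP gap is narrower: the relapse-event entry leaves CSF-only disease unclassified, while the RFS definitions in both documents are broad enough to count it.

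The size of the RFS effect is unknown and probably small. Under the stated assumptions, each subject-month of delayed recognition lengthens the median by about 0.3%. The primary CR/CRh* analysis, the sample size and the interim boundaries do not depend on this rule. The point should be corrected, but it does not threaten the main conclusion.

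**What to change.** - **Protocol 7.2.13:** after the termination sentence, add an exception for isolated CNS leukemia managed under Section 6.6, stated to apply to both relapse and progressive disease.
- **Protocol 8.3.1:** add the same cross-reference.
- **Protocol 6.6:** replace the condition about not having met an event criterion with an explicit one: no bone marrow, peripheral blood or other extramedullary relapse.
- **SAP Section 6, relapse-event entry:** add that CSF-confirmed CNS leukemia after CR/CRh* (or after CRi, for the sensitivity analysis) is an extramedullary relapse and an RFS event on the date of the first positive sample, whether or not treatment continues.

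The cost is three short protocol edits and one SAP sentence. No new data, visits or subjects are needed. Estimated RFS may be slightly shorter. If treatment has already finished, the SAP sentence is still useful before the RFS update at the final analysis (SAP 8.3).

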7.2.14 Patient Reported Outcomes: EORTC Quality of Life Questionnaire

The PRO questionnaire (EORTC QLQ C30) should be completed by the subject before any other clinical assessments and before receiving any study medications. Subjects who are blind or illiterate may have the PRO questionnaires read to them by the study staff. The study staff, however, cannot interpret any of the questions for the subject. Patient reported questionnaires will be completed as outlined in Schedule of Assessments ([Table 9](#)).

The EORTC quality of life questionnaire (QLQ) is a generic patient reported outcomes instrument for assessing the health related quality of life (HRQoL) of cancer subjects participating in clinical trials.

The EORTC QLQ-C30 is composed of both multi-item scales and single-item measures. These include 5 functional scales, 3 symptom scales, a global health status/QoL scale, and 6 single items. Each of the multi-item scales includes a different set of items. No item occurs in more than one scale. All of the scales and single-item measures range in score from 0 to 100. A high scale score represents a higher response level.

Thus a high score for a functional scale represents a high/healthy level of functioning; a high score for the global health status/QoL represents a high QoL, but a high score for a symptom scale/item represents a high level of symptomatology/problems.

7.2.15 Laboratory Assessments

All screening and on-study laboratory samples will be collected and processed at the investigators local laboratory and analyzed locally or centrally. Chemistry (with the exception of amylase and lipase), creatinine clearance, coagulation tests, hematology, urinalysis, IgG, leukemic blasts, and pregnancy confirmation will be performed locally. Chemistry (amylase and lipase), anti-blinatumomab antibody samples, PK samples,

Approved

cytokine samples, lymphocyte subsets, as well as BM samples for hematological and MRD assessments may be evaluated centrally.

Amgen or the central laboratories will supply containers for sample collection, preparation, packaging, and shipping. Detailed instructions for sample collection, processing, and shipping are provided in the central laboratory manual and/or Amgen-provided training materials. The date and time of sample collection will be recorded in the source documents at the site.

Blood draws should not be done via the central venous access. Exception: If a permanent central line with more than one lumen is used, blood draws can be done via the lumen that is not used for drug administration.

Table 11 below outlines the specific analytes that will be assessed during the study at time points outlined in the Schedule of Assessments (Table 9).

Table 11. Laboratory Analyte Listing

Chemistry	Coagulation	Urinalysis^a	Hematology	Other Labs
Sodium	aPTT and INR	Blood	Hemoglobin	Local:
Potassium		Protein	Hematocrit	Serum or urine
Chloride		Glucose	Reticulocytes	pregnancy
Total protein			Platelets	IgG
Albumin			RBC	CSF analytes
Calcium			WBC	Percentage of
Magnesium			Differential	leukemia blasts in
Phosphorus			• Neutrophils	bone marrow
Glucose			• Lymphocytes	(cytological
BUN or Urea			• Monocytes	assessment during
Creatinine ^b				screening)
Uric acid			Optional:	Central:
Alk phos			• Bands or stabs	Bone marrow
LDH			• Eosinophils	Aspirate/Biopsy ^c
AST			• Basophils	(cytomorphology,
ALT			• Blasts	markers, MRD)
C-reactive protein			• Lymphoblasts	Anti-blinatumomab
Bilirubin (total)			• Myeloblasts	Antibodies
GGT			• Promyelocytes	Lymphocyte
			• Myelocytes	subsets
			• Metamyelocytes	PK
			• Atypical lymphocytes	Cytokines
				MRD
Central Chemistry:				
Amylase				
Lipase				

Footnotes defined on next page

Approved

ALT = alanine aminotransferase; aPTT = active partial thromboplastin time; AST = aspartate aminotransferase; BUN = blood urea nitrogen; CSF = cerebrospinal fluid; D1 = day 1; GGT = gamma glutamyl transferase; IgG = Immunoglobulin G; INR = international normalized ratio; LDH = lactate dehydrogenase; MRD = minimal residual disease; PK = pharmacokinetics; RBC = red blood cell; SFU = safety follow-up; ULN = upper limit of normal; WBC = white blood cell

^a The presence of glucose, protein and blood in urine will be assessed during baseline at D1 before the start of infusion at each cycle, and at the SFU visit

^b Calculation of creatinine clearance will only be required during the screening period if creatinine determined by serum chemistry is ≥ 1.5 ULN

^c The following markers will be analyzed as needed: CD3, CD5, CD10, CD13, CD19, CD22, CD23, CD33, CD34, CD79A, POX, TDT

